- *In the analysis of immunogenicity section, one new template (Template 54) for “Comparisons of GM ratios with corresponding 95% confidence interval between anti-RSV F antibody concentrations (IgG Total) and anti-RSV-A neutralising antibody titers at pre-vaccination (Per protocol set)” has been added for Day 90 and final analysis;*
- *In the analysis of immunogenicity section, one new template (Template 55) for “Exploratory comparisons (GM ratios of fold increase post/pre) with corresponding 95% confidence interval between anti-RSV F antibody concentrations (IgG Total) and anti-RSV-A neutralising antibody titers at Day 30 (Per protocol set)” has been added for Day 90 and final analysis;*

Changes in Amendment 3 mainly include the following.***Changes of TFL/TOC for final analysis***

- *All tables concerned with ‘Incidence and nature of symptoms (solicited and unsolicited)’ have been moved to Annex; such tables for Grade 3 are kept as in-text tables;*
- *Tables of ‘Incidence of solicited local/general symptoms reported during the 7-day (Days 0-6) post-vaccination period’ have been moved to Annex; such tables by maximum intensity are kept as in-text tables and corresponding figures have been newly generated for the final analysis, that is, ‘Percentage of subjects reporting solicited local/general symptoms (any grade / grade 3) during the 7-day post-vaccination period’;*
- *All tables concerned with ‘Percentage of subjects reporting the occurrence of unsolicited symptoms’ have been moved to Annex; Such tables for Grade 3 and/or considered related to vaccination are kept as in-text tables with the simplification by removing the columns of LL and UL;*

- *Tables of ‘Percentage of subjects reporting the occurrence of SAE within the 30-day (Days 0-29) post-vaccination period/throughout the study period’ are kept as in-text tables with the simplification by removing the columns of LL and UL;*
- *All tables concerned with ‘Number (%) of subjects reporting the occurrence of adverse events’ have been moved to Annex;*
- *All tables of ‘Number and percentage of subjects reporting the occurrence of medically attended respiration tract infections (MA-RTIs)’ have been moved to Annex; MA-RTIs reported up to DBF of final analysis is kept as one in-text table with the simplification by removing the columns of LL and UL;*

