11.2.3. Demography

- Age: Age at the reference activity, computed as the number of units between the date of birth and the reference activity. Note that due to incomplete date, the derived age may be incorrect by 1 month when month is missing from the birthdate. This may lead to apparent inconsistency between the derived age and the eligibility criteria/the age category used for randomization.
- Conversion of weight to kg

The following conversion rule is used:

- $\text{Weight in Kilogram} = \text{weight in Pounds} / 2.2$
- $\text{Weight in Kilogram} = \text{weight in ounces} / 35.2$

The result is rounded to 2 decimals.

- Conversion of height to cm

The following conversion rule is used:

- $\text{Height in Centimetres} = \text{Height in Feet} * 30.48$
- $\text{Height in Centimetres} = \text{Height in Inch} * 2.54$

The result is rounded to the unit (ie no decimal).

- Conversion of temperature to °C

The following conversion rule is used:

- $\text{Temperature in } ^\circ\text{Celsius} = ((\text{Temperature in } ^\circ\text{Fahrenheit} - 32) * 5) / 9$

The result is rounded to 1 decimal.

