11.2.5. Safety

- For a given subject and the analysis of solicited symptoms within 7 days post-vaccination, missing or non-evaluable measurements will not be replaced. Therefore the analysis of the solicited symptoms based on the Total Vaccinated Cohort will include only vaccinated subjects for doses with documented safety data (i.e., symptom screen completed). More specifically the following rules will be used:
 - Subjects who documented the absence of a solicited symptom after one dose will be considered not having that symptom after that dose.
 - Subjects who documented the presence of a solicited symptom and fully or partially recorded daily measurement over the solicited period will be included in the summaries at that dose and classified according to their maximum observed daily recording over the solicited period.
 - Subjects who documented the presence of a solicited symptom after one dose without having recorded any daily measurement will be assigned to the lowest intensity category at that dose (i.e., 37.5°C for fever or grade 1 for other symptoms).
 - Doses without symptom sheets documented will be excluded.
- For analysis of unsolicited adverse events, such as serious adverse events or adverse events by primary MedDRA term, and for the analysis of concomitant medications, all vaccinated subjects will be considered. Subjects who did not report the event or the concomitant medication will be considered as subjects without the event or the concomitant medication respectively.
- The preferred route for recording temperature in this study will be oral. For the analysis, temperatures will be coded as follows:

Grade	Temperature for oral, axillary or tympanic route	Temperature for rectal route
0	< 37.5°C	< 38.0°C
1	≥ 37.5°C - ≤ 38.5°C	≥ 38.0°C - ≤ 39.0°C
2	> 38.5°C - ≤ 39.5°C	> 39.0°C - ≤ 40.0°C
3	> 39.5°C	> 40.0°C

Note that for all tables described in this section, the way the percentage of subjects will be derived will depend on the event analysed (see table below for details). As a result, the N value will differ from one table to another.

Event	N used for deriving % per subject for Vaccination phase
Concomitant vaccination	All subjects with study vaccine administered
Solicited general symptom	All subjects with at least one solicited general symptom documented as either present or absent (i.e., symptom screen completed)

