Solicited local symptom	All subjects with at least one solicited local symptom documented as either present or absent (i.e., symptom screen completed)
Unsolicited symptom	All subjects with study vaccine administered
Concomitant medication	All subjects with study vaccine administered

The intensity scale of the following solicited AEs will be assessed as described:

Adverse Event	Intensity grade	Parameter
Pain at injection site	0	None
	1	Mild: Any pain neither interfering with nor preventing normal every day activities.
	2	Moderate: Painful when limb is moved and interferes with every day activities.
	3	Severe: Significant pain at rest. Prevents normal every day activities.
Redness at injection site		Record greatest surface diameter in mm
Swelling at injection site		Record greatest surface diameter in mm
Fever*		Record temperature in °C
Headache	0	Normal
	1	Mild: Headache that is easily tolerated
	2	Moderate: Headache that interferes with normal activity
	3	Severe: Headache that prevents normal activity
Fatigue	0	Normal
	1	Mild: Fatigue that is easily tolerated
	2	Moderate: Fatigue that interferes with normal activity
	3	Severe: Fatigue that prevents normal activity
Gastrointestinal symptoms (nausea, vomiting, diarrhoea and/or abdominal pain)	0	Normal
	1	Mild: Gastrointestinal symptoms that are easily tolerated
	2	Moderate: Gastrointestinal symptoms that interfere with normal activity
	3	Severe: Gastrointestinal symptoms that prevent normal activity

*Fever is defined as temperature $\geq 37.5^{\circ}\text{C}$ for oral, axillary or tympanic route, or $\geq 38.0^{\circ}\text{C}$ for rectal route. The preferred route for recording temperature in this study will be oral.

The maximum intensity of local injection site redness/swelling will be scored at GSK Biologicals according to the standard GSK Biologicals' scoring system for adults:

- 0: ≤ 20 mm
- 1: > 20 mm to ≤ 50 mm
- 2: > 50 mm to ≤ 100 mm
- 3: > 100 mm

The maximum intensity of fever will be scored at GSK Biologicals according to the standard GSK Biologicals' scoring system for adults (via the preferred route for recording temperature in this study which is oral):

- 0: $< 37.5^{\circ}\text{C}$
- 1: $\geq 37.5^{\circ}\text{C}$ to $\leq 38.5^{\circ}\text{C}$
- 2: $> 38.5^{\circ}\text{C}$ to $\leq 39.5^{\circ}\text{C}$
- 3: $> 39.5^{\circ}\text{C}$

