14. ANNEX 4: STUDY SPECIFIC MOCK TFL

The following draft study specific mock TFLs will be used. The data display, title and footnote are for illustration purpose and will be adapted to the study specificity as indicated in the TFL TOC.

Note that there may be few changes between the study specific SAP mock TFL and the final TFLs. These editorial/minor changes will not lead to a SAP amendment.

Template #	Table Title	Macro
Template 1	Number of subjects enrolled into the study as well as the number of subject excluded from PPS analysis with reasons for exclusion	%ELIMLIST
Template 2	Number of subjects vaccinated, completed and withdrawn with reason for withdrawal (Exposed set)	%DROP_SUM (OTH=1)
Template 3	Number of subjects vaccinated, completed and withdrawn with reason for withdrawal (Exposed set)	%DROP_SUM (OTH=0)
Template 4	Number of subjects at each visit and list of withdrawn subjects (Exposed set)	%DROPOUT
Template 5	Summary of demographic characteristics (Exposed set)	%DEMOGRA
Template 6	Summary of demographic characteristics by age category (Exposed set)	%DEMOGRA
Template 7	Number of subjects by center (Exposed set)	%CENTER
Template 8	Number of subjects by center for each age category (Exposed set)	%CENTER
Template 9	Number of subjects by country and center (Exposed set)	%CENTER
Template 10	Deviations from specifications for age and intervals between study visits (Exposed set)	%INT_VAL
Template 11	Summary of vital signs characteristics (Exposed set)	%VITAL_SIGNS
Template 12	Study Population (Exposed set)	%CTR_DEMOG
Template 13	Number of enrolled subjects by country	%FREQ_DIS
Template 14	Number of enrolled subjects by age category	%FREQ_DIS
Template 15	Minimum and maximum activity dates (Exposed set)	%DATE
Template 16	Incidence and nature of symptoms (solicited and unsolicited) reported during the 7-day (Days 0-6) post-vaccination period (Exposed set)	%LOGGEN
Template 17	Daily prevalence of any fever during the 7-day (Days 0-6) post-vaccination period (Exposed set)	%SYMPLLOT
Template 18	Incidence of solicited local symptoms reported during the 7-day (Days 0-6) post-vaccination period (Exposed set)	%FREQ
Template 19	Incidence of solicited local symptoms reported during the 7-day (Days 0-6) post-vaccination period by maximum intensity (Exposed set)	%FREQ
Template 20	Incidence of solicited general symptoms reported during the 7-day (Days 0-6) post-vaccination period (Exposed set)	%FREQ

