***<each group>*:**

30 PreF = 30 µg PreF

60 PreF = 60 µg PreF

120 PreF = 120 µg PreF

Control = Placebo

All=any grade>0 for Fatigue, Gastrointestinal symptoms, Headache and any >37.5°C for Temperature/(Oral)

Related*= any grade>0 for Fatigue, Gastrointestinal symptoms, Headache and any >37.5°C for Temperature/(Oral) considered related to vaccination by the investigator

N=number of vaccinated subjects who returned the diary card

n/% = number/percentage of subjects reporting the AE at least once. Maximum intensity only

95%CI = Exact 95% confidence interval; LL = lower limit, UL = upper limit

Temperatures were coded as follows for adults:

- 0: $< 37.5\text{ }^{\circ}\text{C}$
- 1: $\geq 37.5\text{ }^{\circ}\text{C}$ to $\leq 38.5\text{ }^{\circ}\text{C}$
- 2: $> 38.5\text{ }^{\circ}\text{C}$ to $\leq 39.5\text{ }^{\circ}\text{C}$
- 3: $> 39.5\text{ }^{\circ}\text{C}$

Template 22 Percentage of subjects reporting the occurrence of unsolicited symptoms classified by MedDRA Primary System Organ Class and Preferred Term within the 30-day (Days 0-29) post-vaccination period (Exposed set)

		<each group> N =			
		95% CI			
Primary System Organ Class (CODE)	Preferred Term (CODE)	n	%	LL	UL
At least one symptom					
<each SOC (code)>	<each PT (code)>				
...	..				
...	...				

<each group>:

30 PreF = 30 µg PreF

60 PreF = 60 µg PreF

120 PreF = 120 µg PreF

Control = Placebo

At least one symptom = at least one symptom experienced (regardless of the MedDRA Preferred Term)

N = number of subjects with at least one administered dose

n/% = number/percentage of subjects reporting at least once the symptom

95% CI= exact 95% confidence interval; LL = Lower Limit, UL = Upper Limit

Template 23 Percentage of subjects reporting the occurrence of unsolicited symptoms classified by MedDRA Primary System Organ Class and Preferred Term within the 30-day (Days 0-29) post-vaccination period (Exposed set)

		<each group> N =	
Primary System Organ Class (CODE)	Preferred Term (CODE)	n	%
At least one symptom			
<each SOC (code)>	<each PT (code)>		
...	..		
...	...		

<each group>:

30 PreF = 30 µg PreF

60 PreF = 60 µg PreF

120 PreF = 120 µg PreF

Control = Placebo

At least one symptom = at least one symptom experienced (regardless of the MedDRA Preferred Term)

N = number of subjects with at least one administered dose

n/% = number/percentage of subjects reporting at least once the symptom

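### Read literally, Template 21 counts any fever only above 37.5°C, although the SAP defines and grades fever from 37.5°C and assigns exactly that value to unmeasured fever

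*SAP*

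**What the plan says.** All places are in the current SAP, Amendment 4.

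- **Section 11.2.5 (Safety), definition and grades.** "Fever is defined as temperature $\geq 37.5^{\circ}\text{C}$ for oral, axillary or tympanic route". The grading table and the scoring list in that section both put 37.5°C in Grade 1; Grade 0 is anything below it.
- **Section 11.2.5, fever reported present but never measured.** Such a subject "will be assigned to the lowest intensity category at that dose (i.e., 37.5°C for fever or grade 1 for other symptoms").
- **Annex 4, Template 20** (solicited general symptoms). The first temperature row is labelled as all values of 37.5°C or more.
- **Annex 4, Template 21** (the same symptoms by maximum intensity). The first fever row is labelled only All, with no threshold. The threshold is in the footnote: "All=any grade>0 for Fatigue, Gastrointestinal symptoms, Headache and any >37.5°C for Temperature/(Oral"). The related row has its own footnote: "Related*= any grade>0 for Fatigue, Gastrointestinal symptoms, Headache and any >37.5°C for Temperature/(Oral) considered related to vaccination by the investigator". The grade list a few lines further down the same footnote block starts Grade 1 at 37.5°C inclusive.
- **Annex 4, introduction.** Titles, displays and footnotes of the mock tables are described as illustrative and open to adaptation, and: "Note that there may be few changes between the study specific SAP mock TFL and the final TFLs".
- **Section 9, Amendment 3 changes.** The ordinary solicited-symptom tables go to the annex of the report, while "such tables by maximum intensity are kept as in-text tables". Section 1 records that Amendment 4 again moved many tables between in-text and post-text, so the final placement is not certain.

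**The concern.** For fatigue, gastrointestinal symptoms and headache, Template 21's All row means any grade above 0. For fever it means strictly above 37.5°C, which is not the same thing, because 37.5°C is itself Grade 1. The one value on which the two rules differ is also the value the SAP gives to every fever reported without a measurement.

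Occurrence of each solicited general AE over 7 days is a secondary endpoint (section 4.2). If the footnote governs the count, the any-fever rate in Template 21 is too low, and the report can carry two different any-fever rates from the same data, one in Template 20 and one in Template 21. If the programme in fact counts from 37.5°C, the printed footnote misdescribes the number above it. The text needs correcting in either case.

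**Working it through.** The SAP gives no figure on this point to reproduce. The check is to apply its rules to temperatures around the boundary.

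**Step 1. Which values are treated differently?** The inputs are the grades and fever definition in section 11.2.5, the Template 20 row label and the Template 21 footnote.

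| Maximum (°C) | Grade | Fever by 11.2.5 (≥37.5) | Template 20 All (≥37.5) | Template 21 All (>37.5) |
|---|---|---|---|---|
| 37.4 | 0 | no | no | no |
| 37.5 | 1 | yes | yes | **no** |
| 37.6 | 1 | yes | yes | yes |
| 38.5 | 1 | yes | yes | yes |
| 38.6 | 2 | yes | yes | yes |

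The rules part at 37.5°C only.

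**Step 2. Can that value occur?** It can, in two ways.
- By assignment: section 11.2.5 sets unmeasured fever to 37.5°C.
- By measurement: section 11.2.3 says of converted temperatures, "The result is rounded to 1 decimal". For example, (99.5 − 32) × 5/9 = 37.5°C.

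**Step 3. Does another row of Template 21 recover these subjects?** No. The table has no Grade 1 row for fever, and the row after All starts above 38.0°C.

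**Step 4. Is the strict sign explained elsewhere?** The companion table for local symptoms, Template 19, counts redness and swelling above 20 mm. That matches its Grade 1 boundary, which is itself strict (>20 mm). The temperature boundary for Grade 1 is inclusive, so the same sign does not fit. The strict sign for fever also stands in the Amendment 2 and 3 versions of this template, next to correctly printed ≥ signs, so a reading error in the PDF is unlikely.

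**Step 5. Scale, on assumed counts only.** The SAP plans about 100 subjects per group. Take n = 100 and exact (Clopper-Pearson) 95% CIs, as in section 11.1. The fever counts are invented for illustration.

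| Fevers ≥37.5°C | of which exactly 37.5°C | Rate with ≥37.5°C | Rate with >37.5°C |
|---|---|---|---|
| 5 | 1 | 5.0% (1.6–11.3) | 4.0% (1.1–9.9) |
| 5 | 2 | 5.0% (1.6–11.3) | 3.0% (0.6–8.5) |
| 10 | 1 | 10.0% (4.9–17.6) | 9.0% (4.2–16.4) |
| 10 | 3 | 10.0% (4.9–17.6) | 7.0% (2.9–13.9) |

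Each omitted subject costs one percentage point in a group of 100.

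**Step 6. What is untouched?** Grade 2/3 fever begins above 38.5°C. The rows from 38.0°C upward, the fever desirability index DR2 in Annex 3 and the ranking do not depend on the 37.5°C boundary.

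**The case against.** The strongest reply is that Annex 4 says its footnotes are illustrations to be adapted, so the operative rule is section 11.2.5, which is consistent throughout. Template 21's own grade list agrees with it, and so does the sense of the footnote, where All means any grade above 0 for the other symptoms. On that view the strict sign is a typing slip. Templates 20 and 21 are also assigned to the same macro, whose code is not shown, so the count may well be right already.

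Much of this stands. A reader might infer that cases at 37.5°C will be lost; the documents do not establish that. The loss occurs only if the footnote is followed over section 11.2.5. The reply does not remove the error, though. Template 21's All row carries no threshold of its own, so the footnote is the only place where that row's limit is stated, and the annex introduction does not say which boundary applies.

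Two further inferences should not be drawn.
- **A shown conflict for related fever between the two tables.** Template 20's related row states no threshold, so the explicit conflict between the tables is in the All rows. For related fever, Template 21 conflicts with section 11.2.5 and with its own grade list.
- **A fixed share of fevers lost.** One could assume an exponential excess over 37.5°C with mean 0.3 to 0.5°C and get 1 − exp(−0.1/mean) = 28% to 18% of measured fevers at 37.5°C. Nothing in the SAP supports that distribution, and the formula assumes truncation to one decimal. With rounding, as in section 11.2.3, the same model gives 1 − exp(−0.05/mean) = 15% to 10%, and readings just below 37.5°C that round up would raise it again. No share can be given from the documents.

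**Conclusion.** The inconsistency is real and current, and it is minor. Template 21's footnotes set a boundary that contradicts the fever definition, the Grade 1 limit, the value assigned to unmeasured fever, Template 20 and the template's own grade list. Followed literally, they leave every subject with a maximum of exactly 37.5°C out of the any-fever row, and out of the related-fever row where the fever is judged related. That includes every fever set to 37.5°C for want of a measurement, but their number is not given and may be zero. The consequence is confined to those two rows of one table and to a possible mismatch with Template 20, which still counts these subjects. The primary Grade 2/3 fever endpoint and the ranking of formulations are not affected.

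**What to change.** In both footnote lines of Template 21 (All and Related*), replace the strict limit with ≥37.5°C (oral), so that All equals any grade above 0 for fever as it does for the other symptoms. Confirm that the programmed counts for Templates 20 and 21 use that boundary and give the same any-fever number.

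The cost is two characters in the shell and one programming check. No new data are needed, and under the Annex 4 introduction an editorial change of this kind does not call for a SAP amendment. If the strict limit had been programmed, the Template 21 any-fever and related-fever rates would rise by however many subjects sit at exactly 37.5°C.
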